15 ALIGN CONFIDENTIAL

Mandibular Repositioning

Feature (MRF)

Protocol Number: MRF-002

Both subject and doctor perception will be assessed.

6.2 Sample Size Calculation

[figure not shown]
The sample needed to demonstrate non-inferiority of the Invisalign with MRF to literature is found using a single sided proportion value, with the hypothesis that Ho P=Po and a 80% power is patients.

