3. STUDY PURPOSE AND OBJECTIVES

3.1 Study Objectives

To demonstrate that growing teenagers which present up to full cusp Class II malocclusions can be treated using Invisalign with MRF. The primary objective of the study will be to demonstrate that Invisalign with MRF is not inferior to existing functional appliances to treat up to full cusp Class II malocclusions in growing teenagers. The objective will be met if Invisalign aligners with MRF correct Class II malocclusions at a rate that is not inferior to previously reported repositioning rates. This will be achieved if the median rate of correction using Invisalign with MRF at the end of mandible repositioning is non-inferior to published rates of movement (e.g. 0.42 mm/mo.

to a confidence level of 80%.

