6 ALIGN CONFIDENTIAL

Protocol Number: MRF-002

	The secondary endpoints will be measured by
comparing length of treatment	
Both subject and doctor per	pention will be assessed

Both subject and doctor perception will be assessed.

All statistical comparisons will be conducted to an 80% confidence level.

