4.2 Number of Subjects/ Assignment to Treatment Groups

This study will enroll up to 165 patients. It is recommended that each site enroll a minimum of 10 subjects, to facilitate pooling of the data. It is recommended that each site recruits a minimum of 1 subject to have the occlusal feature set and a minimum of 1 subject

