6. DATA ANALYSIS

Data will be analysed by the Sponsor's statisticians or an identified consultant. The data will be analysed using standard univariate and bivariate techniques.

Significance will be demonstrated to a 80%

confidence level.

6.1 Primary endpoint analysis:

The primary objective of the study will be to demonstrate that Invisalign with MRF is not inferior to existing functional appliances to treat up to full cusp Class II malocclusions in growing teenagers. The objective will be met if Invisalign aligners with MRF correct Class II malocclusions at a rate that is not inferior to previously reported repositioning rates. This will be achieved if the median rate of correction using Invisalign with MRF at the end of the mandible repositioning is non-inferior to published rates of movement (0.42 mm/mo.

The secondary endpoints measured by

comparing the length of treatment

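### Does sizing the trial on a one-sided proportion, when success is judged on a median correction rate, make the stated 80% power meaningless?

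*Combined protocol and SAP*

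**What the plan says.** Section 6.2 describes the sample size for showing non-inferiority to the literature as "found using a single sided proportion value, with the hypothesis that Ho P=Po and a 80% power". The resulting number is not readable (the sentence runs "a 80% power is patients"), and a figure in that section is not shown.

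The success criterion is on another scale. Section 6.1 states: "This will be achieved if the median rate of correction using Invisalign with MRF at the end of the mandible repositioning is non-inferior". Section 3.1 has the same criterion, with the benchmark given as "non-inferior to published rates of movement (e.g. 0.42 mm/mo". In both sections the text breaks off inside the bracket that holds the 0.42 benchmark.

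On method, section 6 says only: "The data will be analysed using standard univariate and bivariate techniques". On the error level, the end of section 3.1 says: "All statistical comparisons will be conducted to an 80% confidence level". Section 4.2 gives an enrolment ceiling: "This study will enroll up to 165 patients".

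**The concern.** A power statement belongs to one test of one hypothesis. Here the calculation names a proportion and the decision rule names a median in mm/month. No readable sentence says what P counts, what P0 is, or which test is applied to the median.

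If P were some unrelated responder share, the 80% would say nothing about the chance of meeting the primary objective. As an illustration, P0 = 0.80 and P1 = 0.90 at one-sided alpha 0.10 need 59 subjects. With 59 subjects and normal rates, a sign test of the median has power anywhere from 0.25 to 0.96 as the true median moves from 0.1 to 0.5 SD above the limit.

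If the deciding test were a signed-rank or t test, the real power would also differ from 80%. And if no test were fixed in advance, it could be picked after the data were seen, which matters more than usual in a non-randomized study compared with published rates.

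**Working it through.** **Can the stated figure be reproduced?** No. The calculated N, P0, P1 and the margin are all unreadable. The 80% can be neither confirmed nor contradicted. What can be checked is whether a proportion calculation can serve a median criterion, and how much the choice of test matters.

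**Step 1: are the two descriptions compatible?** Let L be the non-inferiority limit (0.42 mm/month less any margin) and P the share of subjects whose rate exceeds L. For a continuous rate, the median equals L exactly when P = 0.5, and the median is above L exactly when P > 0.5. A one-sided test of P = P0 with P0 = 0.5 is therefore the sign test of the median. The order-statistic confidence limit for the median is the same procedure. P = P0 is then a proper boundary null, and one-sided is the right direction for non-inferiority.

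**Step 2: do the two formulas agree?** Assumptions: margin 0.042 mm/month (10% of 0.42), true median 0.42, normal rates, one-sided alpha 0.20, power 80%, so both z values are 0.8416.

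- Proportion formula: n = [(0.8416 × 0.5 + 0.8416 × √(P1(1 − P1))) / (P1 − 0.5)]², with P1 = Φ(0.042/SD).
- Median formula: n = (2 × 0.8416)² × (SD/0.042)² × π/2.

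| SD (mm/month) | P1 | n, proportion formula | n, median formula | Rounded up |
|---|---|---|---|---|
| 0.10 | 0.663 | 25.3 | 25.2 | 26 |
| 0.15 | 0.610 | 56.8 | 56.8 | 57 |
| 0.20 | 0.583 | 101.0 | 100.9 | 101 |

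Sizing on a proportion is a legitimate way to size a test of a median.

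**Step 3: how much does the choice of test matter?** Assumptions: n = 165 (the ceiling in section 4.2, not the N from 6.2), one-sided alpha 0.20, normal rates, true median 0.42, and d = margin/SD varied because neither is readable. The exact sign test rejects when at least 89 of 165 exceed L, which has size 0.175. Its power is P(Bin(165, Φ(d)) ≥ 89). The t test uses the noncentral t on 164 df. The signed-rank figures come from 20,000 simulated samples for each d. The size-0.20 sign test also rejects at a count of 88 with the probability that brings its size to 0.20.

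| d | Exact sign (size 0.175) | Sign at size 0.20 | Signed-rank | t test |
|---|---|---|---|---|
| 0.10 | 0.536 | 0.572 | 0.657 | 0.671 |
| 0.15 | 0.727 | 0.755 | 0.852 | 0.861 |
| 0.20 | 0.868 | 0.885 | 0.954 | 0.958 |

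The exact sign test trails the t test by 9 to 13 points, but part of that is its smaller size. At equal size the gap is 7 to 11 points.

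**Step 4: is the direction stable?** No. If the 80% confidence means a two-sided interval, one-sided alpha is 0.10. The exact sign test then has power 0.353, 0.553 and 0.741, and the t test 0.500, 0.739 and 0.900. The distribution also matters. At sample sizes set by the proportion formula (P1 from 0.60 to 0.70, alpha from 0.05 to 0.20), exact sign-test power is 0.73 to 0.81. Under normal rates the signed-rank test has 0.89 to 0.92 and the t test 0.90 to 0.93. Under Laplace rates the signed-rank test falls to 0.77 to 0.81 and the t test to 0.63 to 0.75. The sign test can equal or beat either when tails are heavy.

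**The case for a change.** The case for asking for a change is that both halves of the mismatch are in readable text and neither section refers to the other. Even with a sign test, the 80% applies only if P0 is 0.5, P is counted against the right limit and alpha matches. The cure would be a sentence or two and no extra patients.

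The observation stands: the readable text does not state the link. The inference from it does not. The unreadable stretches fall where P, P0, the margin and the test would naturally be defined: within the bracket holding the benchmark in sections 3.1 and 6.1, and in the number and figure of section 6.2. The worry about choosing the test after seeing the data rests on the same unreadable text. The unrelated-responder-share reading is possible, but nothing readable supports it, and section 6.2 says its calculation is for the same non-inferiority aim as section 6.1.

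The power differences are real but depend on a margin, SD, N, alpha and distribution that nobody outside the sponsor can read. They show that tests differ in efficiency, not that the stated figure is wrong.

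**Conclusion.** No change to the plan follows. A one-sided proportion calculation and a median criterion are compatible through the sign test, and the public text contains no figure that this contradicts. What is left is a missing line of explanation that an analyst can supply sensibly: read P as the share above the limit with P0 = 0.5, and test the median with that sign test or an equivalent.

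Another valid one-sample test would also support a sound conclusion. The choice is a trade-off. The sign test needs no symmetry assumption. Under normal rates it gives up about 7 to 11 points of power against the t test at equal size, and under heavy tails that cost can vanish or reverse. These sizes assume 165 analysed subjects, one-sided alpha 0.20 and margin/SD between 0.10 and 0.20. They are illustrations, and they do not show that the trial is under- or over-powered.

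The conclusion would change only if the full text defined P as something other than the share of subjects above the non-inferiority limit, or set P0 at a value other than 0.5.

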7. SAFETY INSTRUCTIONS AND GUIDANCE

7.1 Clinical Adverse Events

An adverse event (AE) is any unwanted dental occurence which a subject experiences during a clinical investigation, whether or not the AE is suspected of having a causal relationship with study treatment. Pre-existing dental events, which increase in frequency or severity or change in nature during or as a consequence of use of an appliance clinical trials, will also be considered as adverse events.

An adverse event will not include non-compliance, lost or abuse of aligners which includes soaking of aligners in any substance or cutting of aligners without the permission of the treating orthodontist. This also includes a subject eating or drinking while wearing their aligners.

16

Mandibular Repositioning

Protocol Number: MRF-002

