7.1.1 Assessment of Adverse Events

All AEs assessed by the investigator shall contact Align Clinical Research group and provide to Align information about the AE. This includes the date of onset and resolution, severity, causality (relationship to aligners), outcome and action taken with respect to study appliance. In addition, the events will be assessed by Align Clinical Research to see if it meets the definition of a serious adverse event (SAE). A serious adverse event will be defined as:

- Led to a death
- Led to a serious deterioration in the health of the subject that:
 - o Resulted in a life-threatening illness or injury
 - \circ Resulted in a permanent impairment of a body structure or a body function \circ Required
 - in-subject hospitalization or prolongation of existing hospitalization \circ Resulted in

medical or surgical intervention to prevent permanent impartment to body structure or a body function

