7.1.2 Treatment and Follow-up of AEs

Any AE will be followed until a satisfactory result is reached or until it becomes stable or until it is proven that it resulted from another cause (concurrent condition) and clinical judgment concludes that further evaluation is not indicated.

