7.2 Handling of Safety Parameters

7.2.1 Reporting of Adverse Events

Each investigator will report any AE (whether or not a relationship to aligners is suspected) with an onset date, after signing the informed consent form and follow this subject until the last aligners are worn, to the Align Clinical Research group at the following e-mail:

The Investigator will need to report observations and findings potentially relevant to the final outcome of an AE in the subject's medical record.

The Sponsor may request return of the involved device or any potential device-related event, for investigation. A procedure for cleaning and returning of the device will be provided by the Sponsor.

The Sponsor will discuss all AEs and initiate and coordinate the appropriate actions. This includes in particular the notification of the competent authority in case of a device-related AE and - in accordance with the Declaration of Helsinki – the notification of the responsible ethics committee for all SAEs.

Mandibular Repositioning

Protocol Number: MRF-002

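### Section 7.1 limits adverse events to undefined dental occurrences and every later step in section 7 depends on that definition, so clearly non-dental events have no stated route there and jaw-joint events are ambiguous

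*Combined protocol and SAP*

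**What the plan says.** Two sentences in section 7.1 say what counts as an adverse event. The first is "An adverse event (AE) is any unwanted dental occurence which a subject experiences during a clinical investigation", regardless of suspected cause. The second adds "Pre-existing dental events, which increase in frequency or severity or change in nature". The rest of 7.1 lists what is not an AE: non-compliance, lost or misused aligners, and eating or drinking with aligners in place.

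Section 7.1.1 has investigators pass AEs to the sponsor's clinical research group and then says "the events will be assessed by Align Clinical Research to see if it meets the definition of a serious adverse event (SAE". The seriousness criteria include death and "Led to a serious deterioration in the health of the subject that", with sub-items such as "Resulted in a permanent impairment of a body structure or a body function".

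Section 7.1.2 says "Any AE will be followed until a satisfactory result is reached". Section 7.2.1 says "Each investigator will report any AE (whether or not a relationship to aligners is suspected", and has the sponsor notify the authority of device-related AEs and the ethics committee of SAEs. It also contains a device-return clause: "The Sponsor may request return of the involved device or any potential device-related event, for investigation".

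**The concern.** Causality is drawn widely, since an AE counts whether or not it is linked to the aligners. The type of event is drawn narrowly, by one adjective that is not defined. Anything that a site does not regard as dental falls outside the starting definition, and so outside all that follows from it.

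The restriction sits badly with this device. Section 2.1 describes interlocking ramps that keep the mandible protruded, and section 1.1 says that appliances of this kind aim at orthopedic or postural change. Section 4.1.2 excludes people with TMD symptoms and people with a known latex and plastic allergy, so the protocol itself treats the jaw joint and allergy as relevant. Section 4.1 makes the safety of repositioning one of the things the study is designed to measure, and allows the data to be used for regulatory purposes. If sites read the adjective differently, the same jaw-joint or allergic event could be reported at one site and not at another.

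**Working it through.** No arithmetic applies, and the plan gives no figure to reproduce. The check follows the definition through section 7.

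**Step 1: the starting definition.** Section 7.1 has two inclusion sentences. Both carry the word *dental* (2 of 2).

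**Step 2: is the word defined?** Section 3.2 has 18 readable rows and none defines it. The AE and SAE rows only expand the abbreviations. TMD has its own row as a joint dysfunction, with nothing on whether it counts as dental.

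**Step 3: what each later step takes as input.**
- Sponsor contact (7.1.1): AEs.
- Seriousness screen (7.1.1): the events just passed to the sponsor, which are AEs.
- Follow-up (7.1.2): any AE.
- Investigator reporting (7.2.1): any AE. The words on suspected relationship widen causality, not event type.
- Notification (7.2.1): device-related AEs and SAEs, both downstream of 7.1.

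All five steps take AEs as defined in 7.1, or SAEs drawn from them.

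**Step 4: wording that might open another route.** The device-return clause speaks of a potential device-related event, which is broader than AE. But it lets the sponsor ask for the device back and puts no reporting duty on the investigator. The list of seriousness criteria could be read as free-standing, but the sponsor assigns SAE status from what it has received, and the readable text has no separate instruction to investigators to report an SAE.

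**Step 5: three example events.**
- Systemic allergic reaction: not dental in any ordinary sense, so not an AE under 7.1. None of the five steps applies.
- Hospital admission for a cause unrelated to the teeth or mouth: the outcome matches a seriousness criterion, but the event never reaches the screen because it is not an AE.
- New jaw-joint, muscle or oral soft-tissue complaint: an AE if the site reads *dental* broadly, not one if it reads it narrowly. The text does not settle which.

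**The case against.** The strongest reply is that the wording is loose but workable. Much of that stands.

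- A reader might infer that 7.1 and 7.1.1 contradict each other, because the seriousness criteria concern general health. They do not. Section 7.1 describes the kind of event and 7.1.1 describes what it led to. A dental infection, for instance, could lead to hospitalization, so whole-body outcomes applied to dental events are coherent.
- A reader might infer that jaw-joint and muscle events are excluded. The documents do not say so. The explicit exclusions in 7.1 do not mention them, the assessor is the treating orthodontist (3.2), and screening in 4.1.2 relies on a dental history exam even though eligibility covers TMD symptoms and allergy. These points favour a broad reading without establishing it. The right word is ambiguous.
- A reader might infer that the whole trial lacks a route for non-dental events, or that its safety data will be incomplete. That goes further than the available text allows. Sections 9, 10 and 13 are not in it, section 14.4 has no readable content, and most visit procedures and Table 1 are not shown. Section 11.1 also binds investigators to 21 CFR Part 812 in general terms. A wider rule elsewhere cannot be excluded.

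What the reply does not meet is the clearly non-dental event. No broad reading of the adjective comfortably covers a systemic allergic reaction or a general hospitalization. Section 11.1 neither amends nor refers to the definition in 7.1, and recording an event on a form would not by itself make it an AE under 7.1.

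**Conclusion.** The point holds, limited to the readable text of section 7. Clearly non-dental events have no stated route to sponsor contact, seriousness screening, follow-up, reporting or notification. Jaw-joint, muscle and oral soft-tissue events are left ambiguous. This is a stated rule and not merely absent detail: a site that followed section 7 to the letter would capture less than a study of mandibular repositioning safety needs.

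Its size is that of the wording: both inclusion sentences and all five dependent steps. The documents give no event rates, so no number of affected subjects can be put on it, and nothing here shows that any event was or will be missed. The conclusion assumes that *dental* carries its ordinary meaning and that the sections and forms that cannot be read do not widen the definition. If they do, a cross-reference from 7.1 to that rule would be enough. The change should be made, but the point is not a contradiction that makes the plan unworkable.

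**What to change.** Add two statements to section 7.1:

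1. Adverse events include jaw-joint (TMD), muscle, oral soft-tissue and allergic events.
2. Any event that meets a seriousness criterion in 7.1.1, dental or not, is reportable and goes through 7.1.1, 7.1.2 and 7.2.1.

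Deleting the word *dental* altogether would be too much. Because 7.1 does not depend on causality, every minor unrelated illness in a teenage population would become an AE to be reported and followed.

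The cost is amendment wording, IRB submission under section 12, a memo to sites, a revised AE form if the present one is too narrow, and a small number of extra reports to process and follow. No new visit or procedure is needed.

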7.1.1 Assessment of Adverse Events

All AEs assessed by the investigator shall contact Align Clinical Research group and provide to Align information about the AE. This includes the date of onset and resolution, severity, causality (relationship to aligners), outcome and action taken with respect to study appliance. In addition, the events will be assessed by Align Clinical Research to see if it meets the definition of a serious adverse event (SAE). A serious adverse event will be defined as:

- Led to a death
- Led to a serious deterioration in the health of the subject that:
 - o Resulted in a life-threatening illness or injury
 - \circ Resulted in a permanent impairment of a body structure or a body function \circ Required
 - in-subject hospitalization or prolongation of existing hospitalization \circ Resulted in

medical or surgical intervention to prevent permanent impartment to body structure or a body function

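### Section 7.1.1 names only the sponsor as judge of whether an adverse event is serious, and ethics committee notification in section 7.2.1 follows that judgement

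*Combined protocol and SAP*

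**What the plan says.** Section 7.1.1 has the investigator contact the sponsor's clinical research group about each adverse event and lists what to supply: "This includes the date of onset and resolution, severity, causality (relationship to aligners), outcome and action taken with respect to study appliance". Seriousness is not on the list. The section then says that, in addition, "the events will be assessed by Align Clinical Research to see if it meets the definition of a serious adverse event (SAE", and gives the definition: death, or serious deterioration in health shown by life-threatening illness or injury, permanent impairment, hospitalisation, or intervention to prevent permanent impairment.

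Section 7.2.1 sets the flow of information. "Each investigator will report any AE (whether or not a relationship to aligners is suspected") to the sponsor's group. "The Sponsor will discuss all AEs and initiate and coordinate the appropriate actions", which include in particular "the notification of the competent authority in case of a device-related AE" and "the notification of the responsible ethics committee for all SAEs".

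The visible text gives no investigator seriousness judgement and does not say what happens if the site and the sponsor differ.

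**The concern.** Section 3.2 identifies the investigator as the treating orthodontist, who sees the subject. The sponsor works from what the site sends. Two of the SAE criteria, permanent impairment of a structure or function and intervention to prevent it, call for clinical judgement, so two competent assessors could differ. The plan settles any difference by silence: only the sponsor's classification has a stated consequence.

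The sponsor also makes the device, and it or its designated statistician analyses the data (sections 4.1 and 6). Section 4.1 gives safety as one of the things the study is designed to measure, and section 4.1.2 admits subjects from 11 to 19 years of age. What is at stake is whether the ethics committee hears of an event that the treating clinician considers serious, and whether that event appears as an SAE in the study's safety record. Nothing in the visible text requires the difference of opinion to be recorded.

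**Working it through.** No arithmetic applies. The check sets sections 7.1.1 and 7.2.1 side by side and follows an event through them.

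1. **Site to sponsor (7.2.1).** Every adverse event is reported, related or not. The site applies no seriousness filter, so no event is lost here.
2. **Content of the report (7.1.1).** The investigator gives timing, severity, causality, outcome and action on the appliance. Severity is listed but seriousness is not, and the SAE definition in the same section does not turn on severity grade.
3. **Classification (7.1.1).** The sponsor's clinical research group is the only party named as assessing the event against the SAE definition.
4. **Onward notification (7.2.1).** The ethics committee is told of SAEs. The competent authority is told of device-related events, with seriousness playing no part.

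Taking steps 3 and 4 together, the four combinations of opinion give:

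| Investigator's view | Sponsor's view | SAE under 7.1.1, ethics committee told under 7.2.1 | Competent authority told | SAE and ethics committee told under an either-party rule |
|---|---|---|---|---|
| Serious | Serious | Yes | If device-related | Yes |
| Serious | Not serious | **No** | If device-related | **Yes** |
| Not serious | Serious | Yes | If device-related | Yes |
| Not serious | Not serious | No | If device-related | No |

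Only the second row changes. Within that row, a device-related event still reaches the competent authority but misses the ethics committee. An event judged unrelated to the device triggers neither of the two notifications that 7.2.1 names.

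**The case against.** The strongest reply is that the sponsor's step is introduced as an addition to what the investigator has assessed. Nothing bars the site from saying that it thinks an event is serious. The sponsor judges from clinical information supplied by the site, and criteria such as death or hospitalisation are largely factual and would show in the report. The two notifications in 7.2.1 are named as particular examples, so the sponsor could tell the ethics committee of other events too. The adverse event form is not visible, section 14.4 has no visible text, and the form may already carry a seriousness field. Section 11.1 also binds investigators to the principles of 21 CFR Parts 812, 50 and 56, whose reporting rules are not reproduced and cannot be relied on either way.

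Much of this stands, and it rules out several stronger readings that a reader might infer:

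- *The sponsor decides alone, with the investigator excluded.* The text names one assessor; it does not forbid another opinion. Exclusivity is an inference from silence.
- *Sites may hold a report until the event is over, because resolution and outcome are listed.* A list of data items is not a timing rule. Section 7.1.2 says "Any AE will be followed until a satisfactory result is reached or until it becomes stable", which fits reporting followed by follow-up.
- *The plan sets no reporting deadline.* None is visible, but the document is heavily redacted, so this point does not rest on it.
- *A serious event could go wholly unreported.* All adverse events reach the sponsor, and the competent authority route does not depend on seriousness.
- *The effect can be put as a percentage of the enrolled subjects.* Any such figure would be hypothetical, and no visible analysis is defined on an SAE rate.

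What the reply does not remove is that, on the stated rule, an investigator's view that an event is serious has no listed place in the report and no stated effect on classification or notification.

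**Conclusion.** The point holds in a limited form. As written, the sponsor's classification decides whether an event is an SAE, and hence whether 7.2.1 calls for the ethics committee to be told. It bites in one situation only: the treating investigator considers the event serious and the sponsor does not. How often that would happen cannot be estimated from the documents. The consequence for each such event is plain: it is not counted as an SAE and is not notified to the ethics committee by that route.

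The conclusion assumes that the list in 7.1.1 is complete as printed; it reads as a whole sentence with no visible gap. It also assumes that no removed section or unseen form contains an investigator seriousness judgement or a rule for disagreement. The change is worth making because it is cheap and makes the safety record less dependent on an interested party that has not examined the subject. It does not touch the primary endpoint or the sample size.

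**What to change.** In section 7.1.1:

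- Add to the information supplied by the investigator a judgement on whether the event meets the SAE definition.
- State that an event is counted and notified as an SAE if either the investigator or the sponsor judges that it meets the definition. The sponsor may raise a non-serious event to serious but may not lower the investigator's serious classification.

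Section 7.2.1 then needs no change, because its SAE trigger takes in both judgements.

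The cost is a sentence or two of protocol text, one item on the adverse event form if it is not already there, and submission of the modification to the Institutional Review Board under section 12. The small downside is that a few more events may be counted and notified as SAEs, including some that the sponsor would have classed as non-serious. The sponsor's differing opinion can be recorded beside the investigator's.
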